6.12.4. Vital Signs and Other Physical Findings

The analysis of vital sign parameters is described in the H0P-MC-CPMP SAP Version 5. Supine, standing, and orthostatic vital signs data will be summarized by treatment, together with changes from baseline, where the baseline is defined as Visit 3 predose assessment. Figures of mean vital signs and mean changes from baseline profiles will be presented by treatment. Additional categorical criteria for abnormal treatment-emergent blood pressure and pulse measurement for adults in BP03 are:

Parameter	Criteria
Orthostatic hypotension (Orthostatic Systolic BP, in mmHg)	Decrease in systolic BP when going from 5 minutes supine to 2-3 minutes standing of ≥ 20 mm Hg
Orthostatic hypotension (Orthostatic Diastolic BP, in mmHg)	Decrease in diastolic BP when going from 5 minutes supine to 2-3 minutes standing of ≥ 10 mm Hg
Orthostatic Pulse Rate (Postural Orthostatic Tachycardia, in bpm)	Increase in pulse when going from 5 minutes supine to 2-3 minutes standing of ≥ 30

6.12.5. Electrocardiograms

The analysis of electrocardiograms parameters is described in the H0P-MC-CPMP SAP Version 5.

The percentages of participants who experienced a treatment-emergent increase from PR interval, QRS interval, and heart rate will be summarized according to CPMP SAP Version 5 Table 6.10. Additionally, the percentages of participants who experienced a PR interval value greater or equal to 240 msec at any time will be summarized.

6.13. Subgroup Analyses

General subgroup analyses are described in the H0P-MC-CPMP SAP Version 5.

There are no additional subgroup analyses planned.

6.14. Protocol Deviations

Patients with study important protocol deviations will be summarized by type of deviation and listed by treatment and investigative site.

Important protocol deviations for the study are described in the H0P-MC-CPMP and H0P-MC-BP03 Trial Issue Management Plans.

6.15. Interim Analyses and Data Monitoring

Safety review will be conducted under the auspices of an Assessment Committee according to the specifications set forth in the protocol. These analyses will be at the CPMP level and will consider data from all ongoing ISAs. Details are provided in the H0P-MC-CPMP SAP Version 5.

No interim analyses are planned for H0P-MC-BP03. If an unplanned interim analysis is deemed necessary, the interim analysis will be conducted under the auspices of the Assessment Committee (AC), and the AC will disseminate interim results, if it is necessary, in a manner that will not affect the conduct of the ongoing study.

6.16. Planned Exploratory Analyses

The following analyses may be conducted for exploratory purposes:

- A frequentist MMRM analysis will be conducted as a sensitivity analysis for the primary and some secondary endpoints.
- A cumulative distribution function of percent change from baseline to endpoint for the RMDQ total score will be provided for each treatment group. However, no statistical comparisons will be made between the groups. The following analysis is to explore different doses of LY3556050:

6.17. Totality of Evidence for Safety

The totality of evidence for safety analysis has been briefly described in the H0P-MC-CPMP SAP Version 5. The key safety events to be considered for H0P-MC-BP03 are listed below by domain:

General Adverse Event Information

- Serious adverse events related to study treatment
- Study discontinuation due to adverse event
- Treatment discontinuation due to adverse event
- Treatment discontinuation due to gastrointestinal disorders
- Treatment discontinuation due to potential nervous system disorder.

Cardiovascular

- QTc prolongation: >60 msec increase
- Serious cardiac disorders adverse event
- Cardiac Failure
- Arrhythmia Event
- MACE
- Hypotension event.

Liver function

- Hy's Law case: Serum total bilirubin ≥ 2 and ALT ≥ 3 for at least one visit during the double-blind treatment period.

Metabolic function

- Serious hypoglycemia adverse event
- Treatment-emergent HbA1c: Shift from low/normal at baseline to high at least once during the double-blind treatment period.

Renal function

- Treatment-emergent abnormal eGFR based on Cystatin C: Shifts
 - Mild at baseline to moderate/severe during the double-blind treatment period
 - Moderate at baseline to severe during the double-blind treatment period
- Serious renal event.

Thyroid

- Hypothyroidism.

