### **1.3. Schedule of Activities (SoA)**

This SoA shows visits and procedures unique to the intervention-specific appendix (ISA) H0P-MC-BP03 (BP03) for LY3556050. Please refer to master protocol and the CLBP DSA SoAs for additional information.

H0P-MC-BP03 ISA	Randomization	Double-Blind Treatment				Early Discontinuation	Notes
Visit Number	V3	V4	V5	V6	V7	ED	
Study Week	0	2	4	6	8		
Visit Window (days)		±3	±3	±3	±3		
Telephone Visit	X a,b						Visit window +2 days There will be 2 telephone visits between Visit 3 and Visit 4: a Visit occurs 4 days after Visit 3 CCI b Visit occurs 8 days after Visit 3 CCI
Procedures							
Evaluate all I/E criteria	X						
Physical examination	X	X	X	X	X	X	V3-V7: Do symptom-directed physical examination
ECG	X	X	X	X	X	X	V3, V5, and V7: Single ECG before in-clinic dosing and at 3 hours after dosing V4, V6 and ED: Single ECG ECG includes collection of PR interval, QRS duration and interval, and heart rate.
Vital signs	X	X	X	X	X	X	Blood Pressure and Pulse Rate V3, V5, and V7: Collect blood pressure and pulse in supine and standing position before in-clinic dosing and at 3 hours after dosing V4, V6, and ED: Collect blood pressure once  Collect orthostatic blood pressure after 5 minutes supine and then 2-3 minutes after standing and collect pulse after supine and standing blood pressure. Temperature and Respiratory Rate Collect once at each visit
Study intervention	X	X	X	X	X		Intervention is taken orally, twice daily, approximately every 12 hours. V3, V5, and V7: Participants take the morning dose in the clinic. Refer to Section 6.6 for dose titration scheme.

H0P-MC-BP03 ISA	Randomization	Double-Blind Treatment				Early Discontinuation	Notes
Visit Number	V3	V4	V5	V6	V7	ED	
Study Week	0	2	4	6	8		
Visit Window (days)		±3	±3	±3	±3		
Telephone Visit	X a,b						Visit window +2 days There will be 2 telephone visits between Visit 3 and Visit 4: a Visit occurs 4 days after Visit 3 CCI [REDACTED] [REDACTED] b Visit occurs 8 days after Visit 3 CCI [REDACTED] [REDACTED].
Procedures							
Intervention compliance		X	X	X	X	X	
Laboratory Tests and Sample Collection							
Hematology	X	X	X	X	X	X	V3: Collect laboratory tests before dosing.
Chemistry	X	X	X	X	X	X	V3: Collect laboratory tests before dosing.
Urine drug screen							Performed at investigator discretion.
Serum pregnancy		X	X	X	X	X	For WOCBP only

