### 7.1. Discontinuation of Study Intervention

#### Cardiovascular Safety

A participant may be permanently discontinued from study intervention for these clinically significant or symptomatic cardiovascular findings

- QTcF >500 msec
- PR interval prolongation >240 msec with symptoms
- symptomatic sustained tachycardia (>120 bpm) or bradycardia (<45 bpm) at rest
- development of a new left bundle branch block, or
- Mobitz type II second- or third-degree atrioventricular block.

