#### **8.1.2. Electrocardiograms**

Single 12-lead ECG will be obtained as outlined in the SoA (see Section 1.3) using an ECG machine that automatically calculates the heart rate and measures PR, QRS, QT, and QTcF intervals.

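### The SAP's QTc key safety event counts only a rise of more than 60 msec, so a participant with a baseline QTcF above 440 msec can pass the protocol's 500 msec level without being counted by that item

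*SAP*

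**What the plan says.** SAP 6.17 introduces its list as follows: "The key safety events to be considered for H0P-MC-BP03 are listed below by domain". Under the cardiovascular domain the only QTc entry is "QTc prolongation: >60 msec increase". It gives no absolute level, and it names neither the correction formula nor the ECG from which the increase is taken.

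Protocol 7.1 (Cardiovascular Safety) works by level. Its list opens with "A participant may be permanently discontinued from study intervention for these clinically significant or symptomatic cardiovascular findings", and the entry at the top is "QTcF >500 msec".

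The data exist. Protocol 8.1.2 specifies a single 12-lead ECG on a machine that "automatically calculates the heart rate and measures PR, QRS, QT, and QTcF intervals".

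For the ECG summaries specific to this study, SAP 6.12.5 says: "The percentages of participants who experienced a treatment-emergent increase from PR interval, QRS interval, and heart rate will be summarized". It then adds a count of participants with a PR interval of 240 msec or more at any time. It adds no such count for QTcF. General ECG analysis, and the general description of the totality-of-evidence analysis, are left to the master SAP (H0P-MC-CPMP SAP Version 5), which is not among the documents supplied.

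**The concern.** A change criterion and a level criterion pick out different participants. Used alone, the change criterion is weakest for those who start high: they need only a modest rise to reach the level that the protocol itself lists as a reason for possible permanent discontinuation.

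Section 6.17 is where the safety evidence is brought together by domain. QTc events will be rare, so one participant can decide whether the cardiovascular domain shows no QTc event or one. A participant who reached the protocol's QTcF level should not be absent from the QTc line because the rise was 57 and not 61 msec.

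QT duration also has some relevance for this compound. The protocol's risk table (2.3.1) reports a concentration-related lengthening of QRS, and the protocol's own abbreviation list defines QT as running from the start of the Q wave to the end of the T wave, so QT contains QRS.

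**Working it through.** The documents state no event count or rate on this point, so there is no figure of theirs to reproduce. The check compares the two rules and then sizes the gap under stated assumptions.

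**Inputs**
- Rule A (SAP 6.17): QTc minus baseline > 60 msec.
- Rule B (protocol 7.1): QTcF > 500 msec.
- Sample size: up to 200 randomized (protocol 9.2, SAP 5.2).
- Distribution of baseline QTcF: not in the documents, so assumed.

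**Step 1: where the rules part.** Take QTc in rule A as QTcF. A participant meets B but not A when 500 < QTcF ≤ baseline + 60. This range is empty unless baseline + 60 > 500, that is, baseline > 440 msec. The boundary is strict: from exactly 440, reaching 501 is a rise of 61 and is counted.

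| Baseline QTcF (msec) | Rise needed to reach 501 | QTcF values above 500 that rule A does not count |
|---|---|---|
| 420 | 81 | none |
| 440 | 61 | none |
| 441 | 60 | 501 |
| 445 | 56 | 501 to 505 |
| 450 | 51 | 501 to 510 |
| 460 | 41 | 501 to 520 |
| 470 | 31 | 501 to 530 |
| 480 | 21 | 501 to 540 |

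Examples: 445 to 502 is a rise of 57, and 470 to 505 is a rise of 35. Both meet rule B and neither meets rule A.

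**Step 2: for how many the gap is possible.** The share is 1 − Φ((440 − mean)/SD) for an assumed normal baseline.

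| Assumed mean, SD (msec) | Share above 440 | Of 200 |
|---|---|---|
| 410, 15 | 0.023 | 4.6 |
| 405, 18 | 0.026 | 5.2 |
| 410, 20 | 0.067 | 13.4 |
| 420, 15 | 0.091 | 18.2 |
| 415, 20 | 0.106 | 21.1 |
| 420, 20 | 0.159 | 31.7 |
| 420, 22 | 0.182 | 36.3 |

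This gives about 2% to 18%. It is the share for whom the gap is arithmetically possible, both arms together.

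**Step 3: roughly how many would fall into it.** The schedule gives 7 on-treatment ECGs: one after dosing at Visit 3, one at Visit 4, two at Visit 5, one at Visit 6 and two at Visit 7. Assume independent changes from baseline with mean 0 and SD s. The expected number with at least one QTcF above 500 msec and no rise above 60 msec is

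200 × ∫ from 440 to 500 of f(b) × [Φ(60/s)^7 − Φ((500 − b)/s)^7] db,

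where f is the assumed baseline density. With s from 12 to 18 msec, the result runs from below 0.01 (mean 410, SD 15, s = 12) to about 2.4 (mean 420, SD 22, s = 18). With a mean shift of 10 msec in every participant and s = 15, it runs from about 0.1 to 3.7. Independence between ECGs is a simplification. The order of magnitude is what matters: between almost none and a few.

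**Step 4: other ways into the 6.17 list.** The remaining items that could catch such a participant are stopping treatment or the study for an adverse event, an arrhythmia event, or one of the serious-event items. All depend on an adverse event being recorded, and the arrhythmia item also depends on how it is coded. Discontinuation under protocol 7.1 is permissive, so a stop is not assured. None of these routes would show the case as a QTc event.

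**The case against.** **The master SAP is not available.** It may name the correction and the ECG baseline, and it may tabulate QTcF above 500 msec. The master protocol or the disease-state addendum may also cap QTc at entry, although the criteria in this protocol's 5.2 do not. This stands as a limit. An entry cap could narrow the gap, and a baseline definition there would settle the reference ECG. A separate tabulation elsewhere would not alter the QTc item that 6.17 spells out for this study.

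**The documents do not contradict each other.** Protocol 7.1 is a rule for the individual; SAP 6.17 is a selected list for group comparison and does not promise to mirror 7.1. Other stopping findings, such as the heart-rate limits, have no numeric item there either, and the risk table names heart rate, PR and QRS but no QT signal. This is fair: the mismatch is a gap in what is counted. But 6.17 does choose to include a QTc item, and 6.12.5 does supply an absolute count for PR, so the missing QTcF level is a specific omission that is easily filled.

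**Stronger readings that the documents do not support**
- *A participant taken off drug for QTcF above 500 msec disappears from the safety assessment.* If an adverse event is recorded, the routes in step 4 are open. Only the QTc item misses the case.
- *QTcF will not be collected.* The schedule note says "ECG includes collection of PR interval, QRS duration and interval, and heart rate", which leaves out QT. But its wording is not exhaustive, and 8.1.2 has the machine measure QTcF. This is at most a matter of tidying.
- *The 3-hour post-dose ECG at Visit 3 might serve as baseline and hide an early effect.* Nothing suggests this. SAP 6.12.4 uses the Visit 3 predose assessment for vital signs taken on the same schedule.

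**Conclusion.** The point holds for the QTc item in SAP 6.17. As written, that item does not count a participant who exceeds 500 msec from a baseline above 440 msec with a rise of 60 msec or less. For baselines of 440 msec or below there is no gap.

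The size is small. A reader might take the 2% to 18% (about 5 to 36 of 200) as participants affected. It is only the share for whom the gap can arise, and it rests entirely on assumed means of 405 to 420 msec and SDs of 15 to 22 msec. Under the further assumptions in step 3, the expected number of missed cases lies between almost none and about 4. The change is still worth making, because the event is rare, each case matters to the reading of the cardiovascular domain, and the correction needs no new data.

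The conclusion does not depend on the assumed distributions; only its size does. It concerns what the analysis counts and does not question the protocol's threshold or its discontinuation rule.

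**What to change.** Reconcile the QTc item in SAP 6.17 with protocol 7.1. Define the event as either of:

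- a treatment-emergent QTcF above the protocol's own level: QTcF > 500 msec on treatment and not above 500 msec at baseline; or
- an increase in QTcF of more than 60 msec from the baseline ECG.

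Name QTcF as the correction, and state the baseline ECG as the Visit 3 predose recording, as 6.12.4 does for vital signs, unless CPMP SAP Version 5 defines it otherwise. The treatment-emergent condition keeps out a participant who was already above 500 msec at baseline and did not change.

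The effect follows from the first table under the check: baselines of 440 msec or below add nothing, a baseline of 450 adds QTcF values of 501 to 510, and a baseline of 470 adds 501 to 530.

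The cost is one added line in the SAP. No new measurement is needed and no clinical rule changes. The downside is that the QTc event count can rise slightly.

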### 2.3.1. Risk Assessment

Potential Risk of Clinical Significance	Summary of Data/Rationale for Risk	Mitigation Strategy
Study Intervention LY3556050		
Cardiovascular	HR: Variable data across clinical studies and across doses PR interval: Concentration-related increase in duration with large variability QRS interval: Concentration-related increase in duration	Vital signs and ECGs evaluated at each visit. Cardiovascular safety parameters to be evaluated include: HR, PR and QRS intervals, and orthostatic vital signs. Additional participant exclusion criteria to protect those with a potential risk. Discontinuation criteria for clinically significant changes.
Thyroid	TSH increases observed in Study LXBA	Labs evaluated at each visit to monitor thyroid function. Additional participant exclusion criteria to protect those with a potential risk. Discontinuation criteria for clinically significant changes.

Abbreviations: ECG = electrocardiogram; HR = heart rate; TSH = thyroid-stimulating hormone.

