**4.2. Scientific Rationale for Study Design**

The master protocol describes the overall study design rationale.

Section 2.3.1 describes elements included in this study to further monitor cardiovascular and thyroid function, and the associated rationale.

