6.12.2. Deaths, Other Serious Adverse Events, and Other Adverse Events for Review

Treatment-emergent adverse events by preferred term will be reported.

In addition to an overall listing, additional lists by terms or organ systems of interest, including cardiovascular, thyroid, and renal functions, will be generated.

The full summary of adverse events is described in the H0P-MC-CPMP SAP. Other adverse events for review coded to Medical Dictionary for Regulatory Activities (MedDRA) terms include

- Hypothyroidism (in SMQ)
- Cardiac arrhythmias (in SMQ)
 - Arrhythmia related investigations, signs, and symptoms
 - Bradyarrhythmia terms, nonspecific
 - Cardiac arrhythmia terms, nonspecific
 - Conduction defects
 - Disorders of sinus node function
 - Supraventricular tachyarrhythmias
 - Tachyarrhythmia terms, nonspecific
 - Ventricular tachyarrhythmias
- Hypotension (in preferred MedDRA term)
 - Orthostatic hypotension
 - Blood pressure ambulatory decreased
 - Blood pressure decreased
 - Blood pressure diastolic decreased
 - Blood pressure systolic decreased
 - Blood pressure orthostatic decreased
 - Dizziness

- Dizziness exertional
- Presyncope
- Syncope
- Abnormal renal function (in MedDRA HLT)
 - Renal function analyses
 - Renal failure and impairment
- MACE (including MI and stroke)
 - Death (preferred MedDRA term)
 - Cardiac arrest (preferred MedDRA term)
 - Cardiac death (preferred MedDRA term)
 - Sudden cardiac death (preferred MedDRA term)
 - Sudden death (preferred MedDRA term)
 - Ischaemic heart disease (SMQ)
 - Ischaemic central nervous system vascular conditions (SMQ)
- Depression (in MedDRA HGLT)
 - Depressed mood disorders and disturbances
- Congestive Heart Failure (in SMQ)
 - Cardiac Failure
- Substance abuse (in MedDRA HLT)
 - Substance related and addictive disorders

Narratives will be provided for patients with the following “notable” events, in addition to the “notable” events listed in the H0P-MC-CPMP SAP.

- Treatment-emergent elevated amylase or lipase $>3x$ ULN
- Renal treatment-emergent adverse events.

CCI

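### Does the key safety event list in SAP 6.17 need measured PR, QRS, heart-rate and TSH events and a fuller Hy's Law definition?

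*SAP*

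**What the plan says.** SAP 6.17 opens by pointing to the master plan: "The totality of evidence for safety analysis has been briefly described in the H0P-MC-CPMP SAP Version 5". It then lists BP03's key safety events by domain. The cardiovascular domain has six items, of which only one is an explicit ECG measurement: "QTc prolongation: >60 msec increase". The others are serious cardiac disorder adverse events, cardiac failure, arrhythmia event, MACE and hypotension event. The thyroid domain has one item, hypothyroidism. The liver domain has one item, Hy's Law, defined as "Serum total bilirubin ≥ 2 and ALT ≥ 3 for at least one visit during the double-blind treatment period".

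Protocol 2.3.1 names two drug-specific risks. On the cardiovascular side it cites variable heart-rate data, a concentration-related QRS increase and, for PR, "PR interval: Concentration-related increase in duration with large variability". It adds: "Cardiovascular safety parameters to be evaluated include: HR, PR and QRS intervals, and orthostatic vital signs". On the thyroid side it cites "TSH increases observed in Study LXBA". Protocol 4.2 refers back to this table: "Section 2.3.1 describes elements included in this study to further monitor cardiovascular and thyroid function".

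Three other parts of the SAP bear on the point:

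- **SAP 6.12.2** sets out adverse-event groupings under the lead-in "Other adverse events for review coded to Medical Dictionary for Regulatory Activities (MedDRA) terms include". They cover hypothyroidism, cardiac arrhythmias, hypotension, renal function, MACE and cardiac failure, among others.
- **SAP 6.12.4** gives measured orthostatic blood pressure and pulse criteria.
- **SAP 6.12.5** summarises treatment-emergent PR, QRS and heart-rate changes and the percentage of participants with PR of 240 msec or more at any time.

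**The concern.** The list seems to measure the wrong things. QTc is absent from the evaluation list in Protocol 2.3.1, yet it has a numeric criterion in 6.17. PR, QRS and heart rate, which that list does name, have none. HbA1c and eGFR enter as laboratory shifts, whereas thyroid, one of the two named risks, is a single undefined word. If arrhythmia event and hypothyroidism are counted from reported adverse events, a silent PR prolongation or TSH rise would not register in this summary, while a silent QTc, HbA1c or eGFR change would.

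The Hy's Law line adds a programming question. Without a unit or a multiple of ULN the thresholds are bare numbers. If ALT were in U/L (an assumption), the ALT condition taken literally would exclude almost no one. The visit wording could also be read as allowing the two values to come from different visits. What would be at stake is whether the safety summary for a proof-of-concept decision reflects the drug's own signals.

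**Working it through.** No plan figure needs reproducing. The check is a comparison of sections plus some simple counts.

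**1. Composition of the list.** Items by domain: general adverse events 5 + cardiovascular 6 + liver 1 + metabolic 2 + renal 2 + thyroid 1 = 17.

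| Type | Items | Count |
|---|---|---|
| Explicit measured criterion | QTc, Hy's Law, HbA1c shift, eGFR shift | 4 |
| Worded as an adverse event or discontinuation | five general items, serious cardiac disorder, serious hypoglycemia | 7 |
| Named but not defined in 6.17 | cardiac failure, arrhythmia event, MACE, hypotension event, serious renal event, hypothyroidism | 6 |

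Check: 4 + 7 + 6 = 17. No item is an explicit PR, QRS, heart-rate or TSH value.

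**2. The six undefined items.** Five have a near-identical grouping in SAP 6.12.2: cardiac failure, cardiac arrhythmias, MACE, hypotension and hypothyroidism. The sixth, serious renal event, has related renal terms there. The arrhythmia grouping is broad. It includes conduction defects, bradyarrhythmia and tachyarrhythmia terms, sinus node disorders, and arrhythmia-related investigations, signs and symptoms, so an ECG finding reported as an adverse event would be captured. The SAP revision history shows that 6.12.2 was updated and 6.17 added in the same version, which supports reading the two together.

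**3. Two of the four measured items use shorthand as well.** HbA1c moves to high, and eGFR moves between mild, moderate and severe, with no cut-offs printed in 6.17. The revision history places the eGFR shift analyses in 6.12.3, which is redacted. So 6.17 is a short list that relies on definitions given elsewhere.

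**4. Where the measurements are analysed.**

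- *PR, QRS, heart rate.* Under the Protocol 1.3 schedule a completer has ECGs after the first dose at Visit 3 (1), Visit 4 (1), Visit 5 (2), Visit 6 (1) and Visit 7 (2), a total of 7. These data are available to the 6.12.5 summaries.
- *Orthostatic signs.* Covered by measured criteria in 6.12.4.
- *TSH.* Listed under chemistry in Protocol 10.1, which is scheduled at Visits 4 to 7, so 4 post-baseline values per completer. Any TSH categories would naturally sit in 6.12.3, which cannot be seen. Thyroid adverse-event listings are planned in 6.12.2. A participant who meets the two-visit TSH rule in Protocol 7.1 stops study intervention and so is visible in that way.

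**5. Hy's Law scale.** SAP 6.12.2 writes its amylase and lipase criterion as a multiple of ULN. The same convention gives at least 2 × ULN for bilirubin and at least 3 × ULN for ALT. No other scale makes both numbers sensible under a Hy's Law label.

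**6. Hy's Law visits.** Assume that the master chemistry panel contains ALT and bilirubin. With 4 post-baseline visits, a same-visit rule checks 4 pairs per completer. An any-visit rule checks 4 × 4 = 16 pairs, of which 16 − 4 = 12 are from different visits. These are counts of comparisons, not probabilities. The plain reading of two conditions joined by 'and' for at least one visit is that both hold at one visit.

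**7. Scale in participants.** The allocation ratio is redacted. Assuming 1:1 to 2:1, the LY3556050 arm would be 200/2 = 100 to 200 × 2/3 = 133. Each 1% with a measured change not reported as an adverse event would then be 1.0 to 1.3 participants absent from this one list. The documents give no rate to put in place of the 1%, and PR, QRS or heart-rate changes that meet the 6.12.5 criteria would still be counted there.

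**The case for a change.** The strongest case for a change is that 6.17 states drug-specific events, so a general reference to the master SAP does not settle each item. On the likely adverse-event reading, a gap does exist. Protocol 7.1 lists PR above 240 msec only with symptoms, so a participant with a silent PR of 240 msec or more would be counted in 6.12.5 but could produce no 6.17 event. A single TSH value of 10 or more does not meet the two-visit rule either. Hypotension event has two candidate definitions in the visible text: the preferred-term group in 6.12.2, which includes dizziness and syncope, and the measured criteria in 6.12.4. The two could give different counts. The remedy would be a few words and some table rows, with no new data.

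The facts in this case stand; the need for a change does not follow. Protocol 2.3.1 and 4.2 commit the study to monitoring and evaluating these parameters, which the schedule and 6.12.5 do for the ECG measures. They do not commit it to making each parameter a key event. Adding PR, QRS and heart-rate rows would largely repeat 6.12.5 in a second place. Hypotension event sits beside other items that match 6.12.2, so that grouping is the natural choice, and the orthostatic measurements are reported separately in any case. For TSH, a claim of omission would rest on text that is redacted or not supplied.

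**Conclusion.** No change follows. As printed, 6.17 is not self-contained: it omits × ULN, does not spell out the same-visit condition, and gives no cross-reference from its event names to 6.12.2. These are gaps in wording that an analyst would fill in the obvious way. Leaving PR, QRS and heart rate off a short list, when they are summarised as measurements elsewhere in the same SAP, is a matter of presentation.

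The size is correspondingly small. No estimate, decision rule or participant count is shown to change, and the documents give no event rates from which an effect could be calculated. The conclusion rests on three assumptions: the 6.17 event names carry their 6.12.2 meanings, the Hy's Law thresholds are multiples of ULN met at one visit, and the master SAP does not say otherwise. Nothing is concluded about the TSH analysis, because 6.12.3 and the master SAP cannot be read. Printing the ULN multiples and the cross-references would be harmless tidying, but would correct no result.
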